5.5.7 Symbol Digit Modalities Test

The SDMT assesses processing speed, which is considered an important measure of cognitive dysfunction in MS patients. The SDMT is a test where using the reference key, the patient has 90 seconds to pair specific numbers with given geometric figures. The number of correct responses in 90 seconds will be considered the SDMT score. A decrease by 4 points on the SDMT score from baseline (last value before blood donation) represents a clinically significant change in cognitive processing.

The following statistical output will be presented:

Table 15.2.7.1 Summary of SDMT Score – Modified Safety Analysis Set

SDMT score will be summarized including change from baseline by dose group and overall. This summary will be performed by treatment cycle subgroup.

Table 15.2.7.2 Summary Clinically Significant Change in SDMT Score – Modified Safety Analysis Set

Number and percentages of patients with a clinically significant change in SDMT score will be presented by dose group and overall. This summary will be performed by treatment cycle subgroup.

Listing 16.2.9 SDMT Score – Enrolled Analysis Set

SDMT assessment data will be listed.

5.5.8 Clinical Laboratory Evaluation

Clinical laboratory values (hematology, biochemistry and urinalysis) are collected at Visit 1, Visit 7, Visit 13, Visit 15, Visit 16 and unscheduled visits.

The following parameters are collected:

Hematology: complete blood count with differential and platelet count, Coombs test, coagulation studies (PT, PTT, INR) and sedimentation rate. Blood group is assessed only on Visit 1.

Biochemistry: Sodium, potassium, creatinine, eGFR (only at Visit 1), urea, total bilirubin, GGT, ALT/GPT, AST/GOT, alkaline phosphatase, total protein, albumin, lactate dehydrogenase, fibrinogen, CRP, iron, ferritin, haptoglobin.

Urinalysis: specific gravity, pH, glucose, protein, ketones, nitrite, leukocytes and blood. Microscopic analysis for leukocytes, erythrocytes, casts, bacteria in case of positive dipstick result for leukocytes, nitrite, protein or blood.

Urine pregnancy tests will be performed locally at all visits except Visit 6 and telephone interviews only in female patients of childbearing potential.

Hematology and biochemistry test results will be flagged to show whether it is a value below (low), above (high) or within (normal) the reference range. Clinical significance of laboratory values is evaluated by the investigator and in the case of a clinically significant finding, the finding will be recorded as an adverse event.

The following rules will be used in order to include results for numeric parameters with non-numeric results in analysis:

- **C Reactive Protein:** The “<0.6 mg/L” results will be set to 0.59 mg/L (reported value) and 5.6 nmol (standardized value).
- **Glomerular Filtration Rate, Estimated:** Will be categorized into “<60.0”, “60-90”, and “>90.0” [mL/min/1.73m²v] and analyzed as a categorical variable.
- **Bilirubin:** The “<0.1 mg/dL” results will be set to 0.1 mg/dL (reported value) and 1.7 umol (standardized value).

Numeric laboratory parameters will be summarized using standard units.

The following statistical output will be provided:

Table 15.2.8.1.1 Summary of Clinical Laboratory Tests: Hematology – Safety Analysis Set

Table 15.2.8.1.2 Summary of Clinical Laboratory Tests: Biochemistry – Safety Analysis Set

The default summary statistics of clinical laboratory test results will be presented by visit, dose group and overall. The absolute change from baseline (last value before first blood donation) will be presented as well.

Table 15.2.8.1.3 Summary of Clinical Laboratory Tests: Urinalysis – Safety Analysis Set

For categorical test results the number and percentage of patients by categorical test results will be presented by dose group and overall. The percentage will be based on number of patients with non-missing results at each visit. For continued test results the default summary statistics of clinical laboratory test results will be presented by visit, dose group and overall. The absolute change from baseline will be presented as well.

Table 15.2.8.2.1 Clinical Laboratory Tests: Incidence of Hematology Abnormalities – Safety Analysis Set

Table 15.2.8.2.2 Clinical Laboratory Tests: Incidence of Biochemistry Abnormalities – Safety Analysis Set

The number and percentage of patients with Low, Normal, High categories of each laboratory parameter will be presented by treatment and overall. The percentages will be based on the number of patients at the specified visit.

Table 15.2.8.2.3 Clinical Laboratory Tests: Incidence of Urinalysis Abnormalities – Safety Analysis Set

The number and percentage of patients with abnormal values of urinalysis parameters will be displayed in normal/abnormal categories. The percentages will be based on the number of patients at the specified visit.

Table 15.2.8.3.1 Clinical Laboratory Tests: Shift Table of Hematology Results – Safety Analysis Set

Table 15.2.8.3.2 Clinical Laboratory Tests: Shift Table of Biochemistry Results – Safety Analysis Set

Shift tables showing changes in the number and frequency of patients with respect to the normal range between baseline (last value before first blood donation) and Visit 7 and Visit 13 will be provided by the dose group.

Listing 16.2.10.1 Laboratory Data – Hematology – Enrolled Analysis Set

Listing 16.2.10.2 Laboratory Data – Biochemistry – Enrolled Analysis Set

Safety laboratory test results will be listed.

Listing 16.2.10.3 Laboratory Data – Urinalysis – Enrolled Analysis Set

All urinalysis test results will be listed.

Listing 16.2.10.4 Urine Pregnancy Test – Enrolled Analysis Set

Urine pregnancy test results will be listed.

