#### 14.1.5 Visit [REDACTED] [REDACTED] [REDACTED] [REDACTED] [REDACTED] [REDACTED] [REDACTED] End of Treatment (EOT)/ Early Discontinuation (ED) visit

- Physical examination
- Vital signs
- Urinary pregnancy test
- Hematology: complete blood count with differential and platelet count, Coombs test, coagulation studies (PT, PTT, INR) and sedimentation rate
- Clinical chemistry: Sodium, potassium, creatinine, eGFR, urea, total bilirubin, GGT, ALT/GPT, AST/GOT, alkaline phosphatase, total protein, albumin, lactate dehydrogenase, fibrinogen, CRP, iron, ferritin, haptoglobin
- Urinalysis: specific gravity, pH, glucose, protein, ketones, nitrite, leukocytes and blood
- Antigen specificity: collect only 10 ml EDTA blood [REDACTED] and 30 ml EDTA blood [REDACTED]
- Biomarker: collect one serum tube (5 ml)
- **Cranial MRI (contrast enhanced)**; (can be performed +/- 5 days of the visit. If the MRI will be performed before [REDACTED], urinary pregnancy test has to be performed at the site prior to the MRI.
- EDSS
- 9-HPT
- T25-FW
- SDMT
- MS relapse assessment
- Concomitant medication
- Adverse events

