4.4 Visit Names and Labels

Visits will be presented as “Visit X” (where X is visit number) in the statistical output. Early discontinuation visit will be presented separately from scheduled Visit 13 and will be labelled as “ED Visit” in the statistical output.

Unscheduled visits will be numbered based on the preceding scheduled visit, e.g. “U Visit 4.1” for the first unscheduled visit after the scheduled Visit 4. Multiple unscheduled visits after the same scheduled visit will be numbered and labelled sequentially.

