4.8 Visit Windows

No visit windowing will be performed. All data will be analyzed using the nominal visit number

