5.5.3 Magnetic Resonance Imaging

Cranial MRI will be performed as follows; the data will be collected in the eCRF as described below:

	■	■	■	■	■
Number of contrasts enhancing lesions (CEL)	x	x	x		
Number of new/enlarging T2 lesions*		x	x	x	x
Total number of T2 lesions	x				

* New/enlarging T2 lesions are calculated in reference to the previous MRI

Cranial MRI scans without contrast agent can also be performed during unscheduled visits. The number of new/ enlarging T2 lesions observed during unscheduled visit will be documented in the eCRF.

The number of CELs, total or new/ enlarged T2 lesions collected during the scheduled visits will be summarized. All collected data will be listed.

Baseline will be defined as the number of CELs at Visit 1.

Lesion size data will be available from MRI images and will be summarized by visit, dose group, and overall.

When combining the eCRF-based MRI data and the MRI data provided by Jung Diagnostics GmbH (JungD), the following rules will be applied:

- Data collected during an unscheduled visit after a scheduled visit with planned MRI assessments where MRI was not performed will be assigned to that scheduled visit.
- Gad+ lesion data available in the JungD data set will not be used if it is collected during a visit where contrast enhancing lesion (CEL) data collection is not planned.
- Gad+ lesion data available in the JungD data set where CEL data collection was planned and is not available in the eCRF due to data collection issues will be used.

The following statistical output will be presented:

Table 15.2.3 Summary of MRI Data – Modified Safety Analysis Set

The default summary statistics of number of CELs, new/ enlarging T2 and total number of T2 lesions and lesion size as well as change from baseline will be presented by dose group and overall. This summary will be performed by treatment cycle subgroup.

Listing 16.2.5 MRI Data – Enrolled Analysis Set

MRI results will be listed.

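### The laboratory shift tables have no place for early-discontinuation or unscheduled results, so a patient who leaves during treatment has no end-of-treatment shift

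*SAP*

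**What the plan says.** SAP 5.5.8 plans Tables 15.2.8.3.1 (haematology) and 15.2.8.3.2 (biochemistry) as shifts relative to the normal range; these "between baseline (last value before first blood donation) and Visit 7 and Visit 13 will be provided by the dose group". The same section says that laboratory values "are collected at Visit 1, Visit 7, Visit 13, Visit 15, Visit 16 and unscheduled visits". ED is not in that list.

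SAP 4.4 states: "Early discontinuation visit will be presented separately from scheduled Visit 13". It gives ED its own label and numbers unscheduled visits after the scheduled visit they follow. SAP 4.8 applies no windows: "All data will be analyzed using the nominal visit number".

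Protocol 14.1.5 has one assessment list for the "End of Treatment (EOT)/ Early Discontinuation (ED) visit". It includes haematology ("Hematology: complete blood count with differential and platelet count, Coombs test, coagulation studies (PT, PTT, INR) and sedimentation rate") and clinical chemistry. Protocol 14.1.8 also requires both panels at an unscheduled visit for a possible relapse.

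The other laboratory outputs in SAP 5.5.8 are summaries by visit with change from baseline, tables of low, normal and high results with the patients at each visit as denominator, and listings for the enrolled set.

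**The concern.** The protocol treats ED as the counterpart of the end-of-treatment visit, so a patient who leaves early should still contribute a final on-treatment laboratory result. The SAP separates the two visits and then builds the shift from Visits 7 and 13 alone, so the final result has no cell to go into. Results from visits held because of symptoms have none either.

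A shift table is where a reader looks to see who moved out of the normal range. Laboratory change matters in this trial: Protocol 10.2.2 and 13.4.1 name iron deficiency and anaemia after blood donation as risks, and six patients are to donate twice. If someone leaves during treatment, the Visit 13 shift describes only those who stayed. Protocol 16.1.2 says that safety summaries will use all the safety data available.

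**Working it through.** The plan gives no figure to reproduce, so the check traces each kind of result and then counts.

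**Which visit ends treatment.** Protocol 7 gives 16 visits in total, and Protocol 7.2 puts three of them in safety follow-up. 16 − 3 = 13, so Visit 13 is the last treatment-phase visit. This agrees with SAP 4.4, which names Visit 13 as the visit from which ED is separated.

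**Where each result can go in the shift tables:**
- Visits 7 and 13: included.
- ED: not included. It is separate from Visit 13 (SAP 4.4), and nominal visits apply (SAP 4.8).
- Unscheduled: not included. The SAP's only rule for moving unscheduled results is for MRI (SAP 5.5.3), where findings "collected during an unscheduled visit after a scheduled visit with planned MRI assessments where MRI was not performed will be assigned to that scheduled visit". Laboratory data have no such rule.
- Visits 15 and 16: not included, because the shift stops at Visit 13.

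**What this means for a patient:**
- Leaves the study before Visit 7: absent from both shifts, even with an ED panel.
- Leaves between Visits 7 and 13: present at Visit 7, absent at Visit 13, ED panel unused in the shift.
- Stops treatment but stays on the visit schedule: can have both shifts.

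**Scheduled panels.** Visits 7, 13, 15 and 16 are the four scheduled post-baseline laboratory visits. With full attendance of the 9 planned patients there are 4 × 9 = 36 panels, and the shift uses 2 × 9 = 18, or 18/36 = 50%. Both scheduled treatment-phase laboratory visits are used; the unused half is all follow-up. ED and unscheduled panels come on top, in a number not known in advance.

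**Weight of one patient.** Planned group sizes are 2, 3 and 4 (SAP 2.3.1):
- Low: 1/2 = 50%
- Medium: 1/3 = 33%
- High: 1/4 = 25%

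Protocol 9.3.1 provides for replacing some early leavers. A replaced patient who had donated blood stays in the safety analysis set, so that group would have one more member and the shares become 1/3 = 33%, 1/4 = 25% and 1/5 = 20%.

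**The case against.** The shift table is an extra display. Protocol 16.1.2 asks for by-visit summaries and frequency tables and requires no shift. Those by-visit outputs are not limited to Visits 7 and 13, all results are listed, clinically significant findings become adverse events, and with nine patients every profile can be read. SAP 4.4 describes how ED is displayed; it does not delete the data. All of this stands, and it is why the point is minor. It does not supply the missing summary. SAP 5.5.8 does not say whether ED and unscheduled results get rows in the by-visit tables, the table shells are not in the documents, and no described table follows a patient to the worst value.

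A reader might infer that everyone who stops early is left out of the shift analysis. The documents do not support that. Leavers between Visits 7 and 13 keep their Visit 7 shift. Protocol 9.3.3 keeps dosed patients who stop the treatment phase on study and on schedule. Protocol 14.1.9 instead prescribes an ED visit for dosed patients who stop the treatment period, so these two passages need reconciling.

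A reader might also infer that the laboratory findings as a whole are biased towards no change. That holds only if the omitted results are more abnormal than the rest, which is unknown, and then only for the shift display. Nor can a distortion be claimed for an all-patient shift, because the shift tables are planned by dose group with no overall column.

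The last objection concerns the remedy. A worst value over all visits would mix in follow-up, when another disease-modifying therapy may be started (Protocol 7.2) and concomitant medication is unrestricted (Protocol 11.1). It would also pick up results around steroid-treated relapses (Protocol 11.2) and give patients with more visits more chances of an abnormal value. The follow-up part is decisive, so the worst value should be confined to the treatment phase. The rest calls for flagging.

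**Conclusion.** The point holds as a limited gap. As written, the shift tables cannot show an end-of-treatment shift for a patient who leaves the study before Visit 13, or any shift for one who leaves before Visit 7, although the protocol calls for the same panel at ED. Unscheduled results are also outside the shift, and no described table gives a worst post-baseline category. The consequence stays within the shift display.

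One affected patient is 50%, 33% or 25% of the low, medium or high dose group. This assumes the planned group sizes, no replacement, and at least one departure during treatment. The documents give no expected number of departures, and if nobody leaves, only unscheduled and follow-up results are affected. SAP 5.5.8 states no denominator for the shift tables, so the effect on a printed percentage cannot be fixed from the text.

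**What to change.** In SAP 5.5.8:
1. Use the ED result as the end-of-treatment (Visit 13) shift value when the patient left the study during the treatment phase before Visit 13, with a footnote. An ED visit held in safety follow-up does not qualify.
2. Add to Tables 15.2.8.3.1 and 15.2.8.3.2 a shift from baseline to the worst value, lowest and highest separately, over all scheduled, unscheduled and ED results in the treatment phase. The denominator is all patients in the safety analysis set with any post-baseline result in that phase.
3. Show Visits 15 and 16 as separate shift columns and do not pool them into the worst value.
4. Name ED among the laboratory collection points.

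The data are already collected and the existing columns stay. The cost is some programming and the risk that worst values include results taken around a relapse or steroid treatment; these should be flagged. If the database is already locked, the SAP Introduction requires the change to go into an SAP Addendum and be discussed in the study report.

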5.5.9 Vital Signs

Vital signs will be assessed at all scheduled and unscheduled visits except telephone interviews. Vital sign measurements will include blood pressure (systolic and diastolic, mmHg), heart rate (beats/minute) and body temperature (°C). Patients must remain in the same body position for 5 minutes prior to having their heart rate and blood pressure taken.

At Visit 3, Visit 4, Visit 10, and Visit 11 vital signs will be recorded in different time points:

- Within 15 min prior to infusion of 1st bag
- 15 min after infusion start of 1st bag
- End of infusion of 2nd bag
- 1 hour after end of infusion of 2nd bag
- 2 hours after end of infusion of 2nd bag

The following statistical output will be provided:

Table 15.2.9 Summary of Vital Signs – Safety Analysis Set

Vital signs will be summarized including change from baseline at each visit and timepoint by dose groups and overall.

Listing 16.2.11 Vital Signs – Enrolled Analysis Set

Vital signs data will be listed.

5.5.10 Physical Examination Findings

Physical examinations will be performed at scheduled and unscheduled visits as described in Section 1, on relevant body systems (eyes, ears, nose and throat, head and neck, lungs/chest, heart/cardiovascular system, abdomen, skin and mucosae, lymph nodes, musculoskeletal system, nervous system (other findings that are not reflected in the EDSS or not related to MS), other-specified).

Any abnormal physical examination findings will be assessed clinically relevant/not relevant by the investigator in the eCRF.

The following statistical output will be presented:

Table 15.2.10 Summary of Physical Examination Findings – Safety Analysis Set

Number and percentage of patients with normal, abnormal, Not CR abnormal, CR abnormal physical examinations findings will be displayed by visit, dose group and overall. The percentages will be based on the number of patients at the specified visit.

Listing 16.2.12 Physical Examinations – Enrolled Analysis Set

Physical examination findings will be listed.

6 DATA MONITORING

An independent Data Safety Monitoring Board will be established to monitor safety data and the performance of the RED4MS trial.

Details and timing of the DSMB are provided in separate document DSMB Charter.

7 CHANGES TO THE ANALYSIS AS LAID DOWN IN THE PROTOCOL AND MODIFICATIONS

No changes to the analysis as laid down in the CSP, Final 7.0.

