## 6 STUDY OBJECTIVES AND ENDPOINTS

**Table 6-1 Study Objectives and Endpoints**

Primary Objectives	Primary Endpoints

Safety objective
 
To assess the safety and tolerability of CLS12311 in patients with RRMS
	
Primary Safety Endpoint
 
The primary safety endpoint is measured by the number and severity of adverse events (AEs) and serious adverse events (SAEs) and/or worsening of disease measured by clinical (relapses) and imaging (number and size of brain MRI lesions) parameters.

Secondary Objectives	Secondary Endpoints

Safety objectives
 
To assess the safety and tolerability of each dose group of CLS12311
	
Safety Endpoints
 
 
• Incidence of treatment-emergent AEs (TEAEs) and treatment-emergent SAEs (TESAEs) (number and severity) in each dose group
 
• Number of confirmed relapses in the treatment phase in each dose group
 
• Changes in clinical measures of disease severity: EDSS, T25-FW, 9-HPT, SDMT in each dose group.
 

Exploratory Objectives	Exploratory Immunological and Biomarker Measures

To assess biomarkers indicating unwanted immune activation, and
 
To understand the mechanism/s of action of tolerance induction with peptide-coupled RBCs and to identify biomarkers for measuring immune tolerance induction
	
 
• Percentage of patients in each dose group showing a reduction of antigen-specific T cells against the protein(s) they responded to prior to study entry
 
• Changes in predefined serum- and cellular biomarkers including autoantigen-specific T cell responses that would indicate proinflammatory activation.
 

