#### 16.1.1 Analysis Populations

- The enrolled analysis set includes all patients who provided informed consent.
- The safety analysis set (SAF) includes all patients with blood donation for CLS12311 production.

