#### 16.1.2 Safety Analysis

A comprehensive safety evaluation will be performed after all patients have completed the last scheduled visit.

Safety will be assessed through summaries of exposure to blood donation, study treatment, adverse events, changes in laboratory test results, changes in neurological function, vital signs and MS relapses.

The safety data will be listed and summarized using all safety data available.

Adverse events (AE) will be coded using MedDRA and will be presented by primary System Organ Class (SOC) and Preferred Term. The analysis will focus on the treatment-emergent AEs

(TEAE), i.e. AEs which started or worsened after blood donation for CLS12311 production. The frequency of TEAEs by dose group and in total will be summarized by incidences standardized to the number of patients at risk and rates standardized to the total observation time.

Frequencies of TEAEs by dose group and in total will also be presented by relationship to study treatment and by severity. Additional analyses will be performed for SAE, TESA, AESIs (see section 12.1.1.1), AEs leading to discontinuation.

The number and percentages of patients having experienced a centrally confirmed relapse will be presented by dose group and in total.

Descriptive summaries of observed values and changes from baseline will be presented for hematology and biochemistry variables by dose group. Each abnormal value will be flagged to show whether it is a value below or above the reference range and assessed by the Investigator for clinical relevance. The assessments of laboratory variables will be tabulated by visit for each clinical laboratory analyte by dose group and in total (frequency tables).

The assessment of categorical urinalysis variables will be tabulated by visit for each urine parameter by dose group and in total (frequency tables).

Vital signs will be described by summary statistics (by dose group and in total) for measured values and changes from baseline by visit.

The number and percentages of patients with normal/abnormal findings in physical examinations will be presented by visit (by dose group and in total).

Additional safety analyses will examine the changes in clinical parameters like EDSS, 9-HPT, T25-FW and SDMT.

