## 16.6 Patient Selection for Analyses

All safety analyses will be based on the SAF.

Demographic and baseline characteristics will be presented for the SAF population.

All collected data will be presented in the listings.

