Multicenter, Phase Ib/IIa Study on the Safety and Efficacy of Autologous Peptide-coupled Red Blood Cells in Patients with Relapsing Remitting Multiple Sclerosis - RED4MS trial

Sponsor Project Code: RED4MS
Scope Project Code: 0284CE01.MJHB

STATISTICAL ANALYSIS PLAN

Sponsor: **Cellerys AG**
[name]

CRO: **SCOPE International AG**
[name]
[name]

Version: Final 2.0 (03-FEB-2026)

The information provided in this document is strictly confidential. No part of this document may be reproduced, transmitted or copied in any form nor its contents disclosed to the third parties without prior written consent of Cellerys AG or a nominated representative.

--

DOCUMENT REVISION HISTORY

Version Draft 0.1 (07-AUG-2024): the document was created.

Version Draft 0.2 (01-JUL-2025): Document updated after sponsor's review. Notable changes:

- AESI definition and corresponding table added (Section 5.5.1)
- Annualized relapse rate was introduced (Section 5.5.2)
- Analysis of lesion volume was introduced (Section 5.5.3)
- The definition of clinically significant change of T25FW was expanded (Section 5.5.6)
- Update as per CTP Version 7.0
- Removed references to Part A and Part B. All analyses for Part B were removed.

Version Draft 0.3 (11-NOV-2025): Document updated after sponsor's review. Notable changes:

- Added definition of the modified safety analysis set (Section 3.1).
- Clarified that annualized MS relapse rate is calculated based on study participation end until the end of study as opposed to the end of the treatment phase (Section 5.5.2)

Version Draft 0.4 (27-NOV-2025): Document updated after sponsor's review. Notable changes:

- Added treatment cycle subgroups (Section 3.2) which will be used in disease-related endpoint summaries (Sections 5.5.2-5.5.7)
- Added definitions for treatment cycle 1 and treatment cycle 2 (4.6) which will be used in summaries of adverse events (Section 5.5.1)

Version Draft 0.5 (17-DEC-2025): Document updated after sponsor's review. Notable changes:

- Renamed lesion volume to lesion size to correspond to endpoint naming (Section 5.5.3)

Version Final 1.0 (12-JAN-2026): No notable changes.

Version Draft 1.1 (29-JAN-2026): Document updated after the Data Review. Notable changes:

- HLA typing results will not be reported (Section 5.2.1)
- Added rule to consider IMP infusions as not done if the batch number for the IMP bag is "NA" (Section 5.4)

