3 ANALYSIS SETS AND SUBGROUPS

3.1 Analysis Sets

The **enrolled analysis set** (ES) will include all patients who provided informed consent.

The **safety analysis set** (SAF) includes all patients with blood donation (partial/full) for CLS12311 production.

The **modified safety analysis set** (mSAF) includes all patients with an IMP infusion (complete or incomplete).

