 - AEs for which “Other action taken” is documented as “No further blood donations” or “Patient withdrawn from the trial”
- **TEAEs leading to death:** AEs documented as having a “fatal” outcome.

The intensity or severity of an adverse event is defined according to the Common Terminology Criteria for Adverse Events (CTCAE, version 5.0, 2017) and provided in Table 3.

Table 3 Adverse Event Intensity Classification

Intensity	Explanation
Mild (Grade 1)	
 • Asymptomatic or mild symptoms • Clinical or diagnostic observations only • Intervention not indicated
Moderate (Grade 2)	
 • Moderate, minimal, local or non-invasive intervention indicated limiting age-appropriate instrumental activities of daily living (ADL)
Severe (Grade 3)	
 • Severe or medically significant but not immediately life-threatening; hospitalization or prolongation of hospitalization indicated; disabling symptoms limiting self-care activities of daily living
Life-threatening (Grade 4)	
 • Life-threatening consequences: urgent intervention indicated
Death (Grade 5)	
 • Death related to AE or to multiple sclerosis

AEs of special interest are defined as severe AEs (Grade of ≥ 3) which are related to the IMP and occurring within one day following infusion of CLS12311/placebo: dyspnea, tachycardia, fever, chills, malaise, shock, infection, allergic reaction, renal or liver failure. Adverse events of special interest will be assessed by the investigator.

TEAEs will be summarized using crude and exposure-adjusted incidence rates. A crude incidence rate will be calculated as number of patients with a TEAE divided by number of patients at risk (at the beginning of the study). An exposure-adjusted TEAE incidence rate per 1 patient-year will be defined as number of patients who experienced a TEAE divided by the total time from the blood donation until occurrence of the event for those who experienced an event, or the end of the safety follow-up for those who did not, multiplied by 365.25, among patients at risk at the beginning of the study:

$$I_{AE} = \frac{n}{\sum_i t_i} \times 365.25 = \frac{n}{T} \times 365.25$$

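### SAP Section 7 declares no change from the protocol, yet every relapse, MRI and disability summary table is on infused patients only, not on the protocol's safety set

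*SAP*

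**What the plan says.** Protocol 16.1.1 defines two sets: an enrolled set and the safety set. Of the second it says "The safety analysis set (SAF) includes all patients with blood donation for CLS12311 production". Protocol 16.6 then sets one rule without exception: "All safety analyses will be based on the SAF". Table 6-1 makes "worsening of disease measured by clinical (relapses) and imaging (number and size of brain MRI lesions) parameters" part of the primary safety endpoint. Section 16.1.2 lists relapse among the safety summaries and treats EDSS, 9-HPT, T25-FW and SDMT as additional safety analyses.

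SAP 3.1 keeps the SAF and adds an mSAF that "includes all patients with an IMP infusion (complete or incomplete"). SAP 5.5.2 to 5.5.7 and the table list in 9.1 place every relapse, MRI and disability summary on the mSAF. The revision history for Draft 0.3 (11 November 2025) records "Added definition of the modified safety analysis set (Section 3.1"). SAP Section 7, where departures from the protocol belong, reads "No changes to the analysis as laid down in the CSP, Final 7.0".

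On adverse event rates, protocol 16.1.2 asks for "rates standardized to the total observation time". SAP 5.5.1 divides the number of patients with an event by the "total time from the blood donation until occurrence of the event for those who experienced an event", or the time to the end of safety follow-up for patients without one.

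**The concern.** Section 7 tells the reader of the study report whether the analysis followed the protocol. Here it says that it did, although two components of the primary endpoint (relapse and MRI lesions) and all the disability measures use a set that the protocol does not contain.

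Other tables would not pick up the difference. The main adverse event tables stay on the SAF, but protocol 12.1.1.2, 12.1.1.3 and 13.1.1 keep relapses and new MS lesions out of adverse event reporting. An event of that kind in a donor who was never infused would be counted in no summary table. Yet it would lie inside the trial's own observation window, because SAP 4.6, 4.7 and 5.5.1 start the treatment phase, fix the baseline and define treatment emergence by blood donation.

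The documents foresee such donors. Protocol 13.4.6 expects some products not to be released, and protocol 9.3.1 replaces early discontinuations. SAP 5.1.1 allows re-enrolment after discontinuation before infusion, and SAP 5.4 treats an infusion with batch number NA as not done.

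**Working it through.** The plan gives no figure to reproduce: there is no sample size calculation, hypothesis or target rate. The check is a comparison of text, followed by illustrative arithmetic.

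**1. Which set each summary uses**

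| Summary | Protocol 7.0 | SAP Final 2.0 | SAF version in SAP 9.1? |
|---|---|---|---|
| Relapse (15.2.2) | SAF (16.6); primary endpoint | mSAF | No |
| MRI (15.2.3) | SAF (16.6); primary endpoint | mSAF | No |
| EDSS (15.2.4) | SAF (16.6) | mSAF | No |
| 9-HPT (15.2.5.1, 15.2.5.2) | SAF (16.6) | mSAF | No |
| T25FW (15.2.6.1, 15.2.6.2) | SAF (16.6) | mSAF | No |
| SDMT (15.2.7.1, 15.2.7.2) | SAF (16.6) | mSAF | No |
| TEAEs, laboratory, vital signs, physical examination | SAF (16.6) | SAF; TEAEs by intensity also on mSAF | Yes |

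Nine tables move and none has an SAF counterpart. Protocol 16.1.2 names no MRI summary; MRI falls under the 16.6 rule because it is part of the primary safety endpoint.

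**2. What the change of set can do**

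Inputs: 9 planned patients in the first cycle (protocol synopsis), taken as all infused; k donors never infused, an assumption because the documents do not give k. Then SAF = 9 + k and mSAF = 9. For one relapse:

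| k | In an infused patient: SAF | In an infused patient: mSAF | In an un-infused donor: SAF | In an un-infused donor: mSAF |
|---|---|---|---|---|
| 0 | 1/9 = 11.1% | 1/9 = 11.1% | not possible | not possible |
| 1 | 1/10 = 10.0% | 1/9 = 11.1% | 1/10 = 10.0% | 0/9 = 0% |
| 2 | 1/11 = 9.1% | 1/9 = 11.1% | 1/11 = 9.1% | 0/9 = 0% |
| 3 | 1/12 = 8.3% | 1/9 = 11.1% | 1/12 = 8.3% | 0/9 = 0% |

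The effect has no fixed direction. The mSAF gives the higher percentage when the event is in an infused patient, and omits the event when it is in a donor who was not infused.

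**3. The adverse event rate**

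Assume 336 days of observation per patient (48 weeks × 7, from the planned minimum duration in protocol 15.1, here counted from donation).

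- Every patient has a TEAE, the first on day 30. Patients over total observation time: 365.25/336 = 1.09 per patient-year. SAP formula: 365.25/30 = 12.18.
- One of 9 patients has a TEAE. Total observation time: 365.25/(9 × 336) = 0.121. SAP formula: 365.25/(8 × 336 + d), which is 0.136 for d = day 5 and 0.128 for d = day 168.
- If the protocol meant events and not patients, three events per patient would give 3 × 365.25/336 = 3.26.

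The two denominators differ for any patient with an event before the end of follow-up. The gap is small for rare events and large when most patients have an early one. The last line shows that the protocol phrase alone does not fix the rate.

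**The case against.** The case for the SAP has weight.

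- **Choice of set.** Protocol 12.1.1 frames the primary variable as what happens after doses of CLS12311, and the synopsis frames disability change in the same way. Infused patients are a defensible set for those questions. This stands as a reason that Section 7 could give; it does not make the statement of no change true.
- **Visibility.** A reader might infer that an un-infused donor's relapse would be lost altogether. It would not: Listings 16.2.4 and 16.2.5 are on the enrolled set, and in a trial of about nine patients listings carry much of the safety reading. What is lost is the count in the primary-endpoint summary.
- **Double counting.** SAP 5.1.1 summarises each enrolment separately, so a donor who is not infused and then re-enrols can count twice in the SAF and once in the mSAF. SAF percentages are not automatically the better ones.
- **The rate.** A reader might infer that the SAP overrode a defined rate. Protocol 16.1.2 gives no formula or numerator, and 16.1 leaves details to the SAP, so the SAP formula can be read as filling in a loose phrase. The crude incidence agrees with the protocol. What stands is that time to first event is not literally total observation time, and nothing in the SAP says so.
- **Motive.** Because the mSAF arrived six months after protocol 7.0 in an open-label trial, a reader might infer a switch prompted by results. The documents do not support that. The revision history attributes it to sponsor review, the entry precedes those made after data review, and protocol 16.1 allows the SAP to be finalised up to database lock.

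**Conclusion.** Section 7 is incorrect as written. The change of set conflicts directly with protocol 16.6, affects all nine relapse, MRI and disability tables, and covers two components of the primary safety endpoint. This conclusion rests on the text alone.

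The numerical effect is unknown. It is zero if every donor was infused. With one un-infused donor, an assumption, a relapse in that donor moves from 10.0% to 0%, and a relapse in an infused patient moves from 10.0% to 11.1%. All analyses are descriptive, so no error rate or power is affected. The finding is one of undeclared departure and a missing companion table; it does not show that the mSAF is the wrong set.

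The adverse event rate is a lesser point: a difference in denominator that should be disclosed, not an established contradiction.

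**What to change.** 1. In SAP Section 7, replace the statement of no change with an entry saying that the summaries in 5.5.2 to 5.5.7 use the mSAF where protocol 16.6 specifies the SAF, and give the reason.
2. Produce Tables 15.2.2 and 15.2.3 on the SAF beside the mSAF versions, with a footnote identifying any patient counted more than once through re-enrolment. State the number of donors never infused; if it is zero, one sentence saying that the two sets coincide can replace the repeat tables.
3. In the same section, state that the exposure-adjusted rate counts patients with an event and stops their time at the first event, and that the protocol gave no formula.

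The cost is a short paragraph and two repeat tables from existing programs, with no new data. If the database is already locked, the SAP's Introduction provides the route: an SAP Addendum, discussed in the study report.
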